**Pain and use of painkillers**

This endpoint will be analyzed as described above and considering the frequency of physical activity as a subgroup analysis.

**Drug regimen adopted**

This endpoint will be analyzed as described above and considering the frequency of physical activity as a subgroup analysis.

### HRQoL

This endpoint will be analyzed as described above and considering the frequency of physical activity as a subgroup analysis.

### Hospitalization / missed days at school

This endpoint will be analyzed as described above and considering the frequency of physical activity as a subgroup analysis.

### Joint Health Status

This endpoint will be analyzed as described above and considering the frequency of physical activity as a subgroup analysis.

### **To describe severe vs moderate haemophiliac patients for the above mentioned items.**

This endpoint will be assessed by analyzing each of the endpoints above mentioned and considering the severity of disease as a subgroup analysis.

### **To evaluate sleep duration and sleep stages in participant patients.**

The analysis of sleep duration (overall and by stage) will be done as for the primary endpoints described in Section 4.4.1.

### **Bleeding and daily physical activity.**

The relationship between bleedings and physical activity (daily and by type) will be done as described in Section 4.4.1 but considering only data collected by the fitness tracker in the two days preceding the day in which the bleeding occurs.

For the relationship with daily physical activity, only data in the valid days will be considered. For each bleeding, the data collected in the two valid days before the bleeding will be summarized by the median. In case only one valid day is available, those values will be used to summarize the activity done before that bleeding.

All the activities recorded in the two days before the bleeding will be used regardless they occur in a valid day.

**To observe patients, on primary and secondary objectives, for additional 6 months if new therapies become commercially available for patients with Haemophilia A without inhibitors against FVIII, during the course of the study and if patient will start such treatments during the observation period.**

All the analysis proposed in sections 4.4.1 and 4.4.2 (except for the subgroup analyses) will be repeated by considering the start of any newly approved drug for haemophilia A during the study. See Section 4.4.4 for more details on this subgroup analysis.

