- Bleeds starting from the first sign of bleed and ending 72 hours after the last treatment for the bleed, within which any symptoms of bleeding at the same location or injections are ≤ 72 hours apart, are considered the same bleed.
- Any injection to treat the bleed, taken > 72 hours after the preceding injection, is considered the first injection to treat a new bleed at the same location.
- Any bleed at a different location is considered a separate bleed regardless of time from last injection.

Definition of bleed sites:

Sites of bleed will be defined as follows:

Target joints: defined as major joints (e.g., hip, elbow, wrist, shoulder, knee, and ankle) into which repeated bleeds occur (frequency of ≥ 3 bleeds into the same joint over the last 24 weeks prior to study entry), - Muscle bleeds, - Other bleeds.

Definition of bleed types:

The assessment of a bleed will be separated into spontaneous bleeds, traumatic bleeds, and bleeds related to procedure/surgery. Both spontaneous bleeds (i.e., the occurrence of haemorrhage where neither the patient nor a caregiver can identify a reason) and traumatic bleeds (i.e., haemorrhage occurring secondary to an event such as trauma, "strenuous" activity, or "overuse") will be collected.

Types of bleed will be defined as follows:

- Spontaneous bleeds: bleeds should be classified as spontaneous if a patient records a bleed when there is no known contributing factor such as definite trauma, antecedent "strenuous" activity or "overuse" or "procedure/surgery." The determination of what constitutes "strenuous" or "overuse" will be at the discretion of the patient. For example, light jogging may be considered "non-strenuous" while sprinting may be considered "strenuous," lifting of weights for a short period of time may be considered "moderate use" while repetitive weightlifting may be considered "overuse."
- Traumatic bleeds: bleeds should be classified as traumatic if a patient records a bleed when there is a known or believed reason for the bleed. For example, if a patient is to exercise "strenuously" and then has a bleed in the absence of any obvious injury, the bleed would be recorded as a traumatic bleed because, although no injury occurred, there was antecedent "strenuous" activity. Bleeds subsequent to injuries would certainly be classified as traumatic.

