#### **4.1.2 Evaluable population**

The evaluable population will consist of all enrolled patients with at least 6 valid months of physical activity evaluations during the study.

The patients with 6 valid months of physical activity will be defined by the presence of the two following conditions:

- an Extent of Exposure to the fitness tracker of at least 6 months (180 days) (see Section 4.3.1 for the definition of Exposure).

AND

- a compliance to the use of the fitness tracker of at least 50% in the period defined by the extent of exposure (see Section 4.3.2.1 for the definition of the compliance respect to the exposure).

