## **4.4 EFFICACY ANALYSIS**

#### **4.4.1 Co-primary Endpoints**

All the co-primary endpoints presented in Section 2.2.1, i.e.:

- active minutes:
  - heart zone minutes (overall, fat-burn minutes, cardio minutes, peak minutes)
  - active zone minutes (overall, lightly active minutes, fairly active minutes, very active minutes)
  - MVPA minutes
- METs
- number of steps

will be summarized at subject level as median per day (i.e. the median of each parameter will be calculated by using all the valid days collected during the observational period for each subject). Each parameter, derived as median per day at subject level, will be analyzed by means of descriptive statistics as described in Section 4. The 95% confidence interval for the mean will be also displayed.

The statistics will be shown overall and by age groups (12-17, 18-30 and 31-50). The comparison among the age groups will be performed by means of a one-way ANOVA or, if assumptions of normality is not confirmed (by a visual inspection: histogram and qq-plot), by means of a Kruskal-Wallis test.

Daily physical activity will also be summarized:

- by start of any newly approved drug for haemophilia (see Section 4.4.4 for subgroup definition).
- by COVID-19 period on the EVL population (see Section 4.4.4 for subgroup definition).
- by month through the entire observational period on the EVL to observe the impact of COVID-19.

Data will be summarized at subject level considering data collected in each period above-mentioned.

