### **Number, sites and types of bleeds occurring during routine clinical practice and reported at any occurrence via the electronic Patient-Reported Outcome (ePRO) application**

The overall number of bleeds per patients will be analyzed by means of descriptive statistics as described in Section 4. Data will be shown overall and by age group.

Bleeds that occur the same day but in different body site will be counted separately. Number and proportion of patients with no bleeds and 1 or more bleeds will also be shown.

The bleeds will be analyzed overall, by body site (Joint bleeds, Muscle bleeds, Other bleeds) and type (Spontaneous bleeds, Traumatic bleeds, Bleeds related to procedure/surgery).

The 95%CI for the mean number of bleeds will also be shown.

Number, sites and types of bleeds will also be summarized:

- by start of any newly approved drug for haemophilia (see Section 4.4.4 for subgroup definition).
- by COVID-19 period (see Section 4.4.4 for subgroup definition).
- by month through the entire observational period to observe the impact of COVID-19.

Other subgroup analyzes: frequency of physical activity, severity of the disease.

**Treatment regimen for haemophilia A (prophylaxis, preventive treatment before physical activity, treatment for any episode of bleeds), in terms of type of regimen (demand vs. prophylaxis), product used and dose.**

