**Annualized Bleeding Rate (ABR)**

The total number of bleeds (overall, by site and by type) and the total follow-up (person-years) will be displayed. The rate will be derived as ratio between the number of bleeds and total follow-up.

Number and proportion of subjects with at least one bleeding will be also shown.

The exact Poisson 95%CI for the rate will be calculated overall, by site and type.

Other subgroup analyzes: frequency of physical activity, severity of the disease (see Section 4.4.4 for subgroup definition).

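### The only analysis under the exploratory activity-bleeding objective looks at the two days before each bleed and has no bleed-free reference days, so on its own it cannot show an association.

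*SAP*

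**What the plan says.** Protocol section 5.2.2 and SAP section 2.2.2 list, as an exploratory objective, an evaluation of how the type and intensity of activity relate to bleeds. Protocol section 6.7.1 gives no method specific to it. The SAP places one analysis under it, in section 4.4.2 under Bleeding and daily physical activity. It follows section 4.4.1 but "considering only data collected by the fitness tracker in the two days preceding the day in which the bleeding occurs". For daily activity, "For each bleeding, the data collected in the two valid days before the bleeding will be summarized by the median"; if only one of the days is valid, that day's value is used. For activity type, the same two days are used without the valid-day filter.

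Section 4.4.1 supplies the rest of the method. Each endpoint "will be summarized at subject level as median per day", is described with a 95% CI for the mean, and is tested once: "The comparison among the age groups will be performed by means of a one-way ANOVA", or by Kruskal-Wallis if normality is doubtful.

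Three other planned analyses touch the question:

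- Bleed counts carry the line "Other subgroup analyzes: frequency of physical activity, severity of the disease", where the first item means active or sedentary status.
- The annualized bleeding rate has the same split, and "The exact Poisson 95%CI for the rate will be calculated overall, by site and type".
- Bleeds are split by type. Protocol section 6.4.1 counts a bleed after strenuous activity as traumatic, and the decision on what is strenuous "will be at the discretion of the patient".

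The mock shells are in an attachment to the SAP that was not available, so table columns could not be checked.

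**The concern.** A relationship between activity and bleeding needs two quantities: activity before bleeds, and activity at comparable times when no bleed followed. The analysis under this objective produces only the first. Followed exactly, it can show whether pre-bleed activity differs between age groups, but not whether activity is higher, lower or the same before a bleed as at other times. Its output would still appear under a heading that promises a relationship.

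The objective matters to the protocol's own argument. Protocol section 6.2.1 says that little is known about how far activity raises bleeding risk, and presents this population as suitable for assessing that risk.

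The unit of analysis is also unsettled. Section 4.4.2 takes a median per bleed, while the section 4.4.1 method it borrows works on one value per patient. The SAP does not say how repeated bleeds in one patient are handled. If bleeds are pooled, frequent bleeders dominate; patients without bleeds contribute nothing either way.

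**Working it through.** The documents state no figure for this objective, so there is none to reproduce. The check is first structural, then an illustration. The only numerical input from the documents is the 50% compliance floor in SAP section 4.1.2; the rest are assumptions.

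**1. Is a reference supplied anywhere?**

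| Planned analysis | What it compares | Does it fill the gap? |
|---|---|---|
| SAP 4.4.2, Bleeding and daily physical activity | Two-day pre-bleed windows, by age group | No bleed-free or usual-level reference |
| SAP 4.4.1, medians over all valid days | Patients, by age group | Not bleed-free, includes patients without bleeds, no contrast with pre-bleed values planned |
| SAP 4.4.2, bleed counts and bleeding rate by active/sedentary status | Patients, over the whole follow-up | Ignores timing. Status comes from the same follow-up in which bleeds can reduce activity |
| SAP 4.4.2, traumatic versus spontaneous bleeds | Bleeds with bleeds | Attributed by the patient, includes injuries, not tracker-based |
| SAP 4.4.2, treatment for bleeding by pre-bleed intensity | Bleeds with bleeds | No bleed-free days |
| SAP 4.4.3, sensitivity analyses | None planned | Adds nothing |

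No subgroup in SAP section 4.4.4 separates pre-bleed from bleed-free days.

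**2. What a pre-bleed figure alone can mean.** Let q be the share of pre-bleed windows that are active and p the share of reference windows. Then OR = [q/(1−q)] / [p/(1−p)]. With q = 0.60 (assumed), the pre-bleed odds are 0.60/0.40 = 1.5, so p/(1−p) = 1.5/OR:

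- OR 0.5: odds 3.0, p = 0.75
- OR 1: odds 1.5, p = 0.60
- OR 2: odds 0.75, p = 0.75/1.75 = 0.429

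Conversely, p = 0.30 gives 1.5/0.4286 = 3.50 and p = 0.80 gives 1.5/4 = 0.375. The same pre-bleed result fits a raised, unchanged or lowered risk. The same logic applies to medians of minutes, METs or steps.

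**3. Would a comparison have enough usable data?** Evaluable patients need "a compliance to the use of the fitness tracker of at least 50% in the period defined by the extent of exposure". With compliance c and independent days, a two-day window has at least one valid day with probability 1−(1−c)². This gives 0.75, 0.84, 0.91 and 0.96 for c = 0.5, 0.6, 0.7 and 0.8. Clustered non-wear lowers it: at c = 0.5 with day-to-day correlation 0.5, both days are invalid with probability 0.25 + 0.5×0.25 = 0.375, leaving 0.625 usable. The ITT population has no compliance floor.

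**4. Expected precision, by simulation.** Conditional logistic regression, up to four control windows per bleed, binary exposure, each window usable with probability 0.75, true OR 1, 1,000 runs:

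| Bleeds (assumed) | Contributing, about | 95% CI, usual active share 0.3 | 95% CI, usual active share 0.5 |
|---|---|---|---|
| 50 | 37 | 0.44–2.28 | 0.47–2.11 |
| 100 | 75 | 0.56–1.78 | 0.59–1.70 |
| 200 | 149 | 0.67–1.50 | 0.69–1.45 |

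Drawing controls only from usable windows would narrow these somewhat.

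**5. A separate, minor point.** Under Treatment regimen for bleeding (SAP 4.4.2), a two-day median of moderate-to-vigorous (MVPA) minutes above zero is classed as intense activity. The median of two values is their mean, so days of 0 and 1 minute give 0.5 and qualify. If a share p of days has any such minutes (assumed, independent days), 1−(1−p)² of windows with two valid days qualify: 0.51, 0.75 and 0.91 for p = 0.3, 0.5 and 0.7.

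**The case against.** The study is descriptive and was not sized to test a hypothesis. The objective is exploratory, and the protocol promises no effect estimate for it, so the SAP drops nothing that was promised. This limits the weight, but even a description of a relationship needs something to relate the pre-bleed values to.

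A reader could set the pre-bleed medians beside the all-valid-day medians of section 4.4.1. Contamination by pre-bleed days would be small: at an assumed 1, 6 or 12 bleeds a year, two days each is 2/365 = 0.5%, 12/365 = 3.3% or 24/365 = 6.6% of days. That is fair, so the lack of purity is not the main problem. The contrast is still unplanned and not within-patient, and it sets per-bleed values against per-patient values that include patients who never bled.

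The active/sedentary and traumatic/spontaneous splits do bear on the question. It would be wrong to say that the SAP relates activity to bleeding nowhere. Neither split addresses tracker-measured activity shortly before a bleed.

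Some limits of a within-patient comparison stand:

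- A window ending the day before the bleed misses same-day activity.
- Weekday and lockdown period can distort the contrast unless control windows are matched on them.
- Bleeds entered after a monthly prompt may be misdated.
- With few bleeds the estimate may be too imprecise to use.

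These are reasons to specify the comparison carefully or to relabel the output. They do not make the present analysis sufficient.

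**Conclusion.** The concern holds. The analysis placed under the activity-bleeding objective describes activity before bleeds without any reference, so alone it is compatible with a positive, null or negative association. That conclusion follows from the SAP text and does not depend on the assumed shares, which only illustrate it. It would change only if the unseen mock shells define a comparator; the SAP text defines none.

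The point should be fixed, but its weight is limited: the objective is exploratory and the primary endpoint is untouched. Whether a proper comparison would be informative depends on a bleed count that the documents do not give. At an assumed 50 bleeds the interval under no association runs from about half to more than double.

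**What to change.** **Minimum:** if no comparison is added, state that the output describes activity before bleeds and do not call it a relationship. This costs one sentence.

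**Full:** keep the descriptive table and add a within-patient comparison of each pre-bleed window with bleed-free windows from the same patient.

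- Control windows follow the same data rule as the pre-bleed window: valid days for daily activity, and all recorded activities for activity type, with non-wear reported.
- They must not overlap another bleed or a recovery period fixed in the SAP. Matching on weekday and lockdown period is a sensible refinement.
- A case-crossover analysis by conditional logistic regression is one suitable method; a patient-day model with patient effects is another.
- Use MVPA minutes as a continuous variable. Report the estimate with its 95% CI as exploratory, and by activity type only where counts allow.
- State the unit of analysis and the numbers of bleeds and patients contributing.
- Report the timing of preventative or prophylactic treatment only if administration dates are held. The documents state no administration time for these doses, and adherence is a weekly answer; if dates are not held, record this as a limitation.

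For the split under Treatment regimen for bleeding, use MVPA minutes as continuous or relative to the patient's usual level.

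The full fix needs SAP text and moderate programming but no new activity or bleed data: daily tracker records (Protocol 6.1.1) and bleed dates (Protocol 6.4.1) are already collected. The main drawback is possibly wide intervals.

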#### **Physical examination at baseline and every three months.**

Analysis of physical examination data will be performed in the whole sample at baseline and every 3 months.

For each timepoint, the following summaries will be provided:

- Summary tables showing for each parameter the frequency of patients reporting an abnormal (clinically or not clinically significant) value and the frequency of patients reporting a clinically significant value.
- Shift tables presenting the number and the percentage of patients in each bivariate category (baseline versus each post-baseline visit) with regards to investigator's interpretation (normal/abnormal/not done).

#### **Vital signs at baseline and every three months**

Summary statistics will be provided along with summary of the change from baseline at each timepoint for vital signs:

- Weight (Kg)
- Heart rate (beats/min)

### **4.4.3 Sensitivity Analyses**

NA

#### **4.5 PHARMACOKINETIC AND PHARMACODYNAMIC ANALYSES**

NA

#### **4.6 SAFETY ANALYSES**

NA

#### **4.7 MISSING DATA**

The number of patients with missing data will be presented under the “Missing” category, if present. Missing values will not be included in the denominator count when computing percentages. Similarly, only the non-missing values will be evaluated for computing summary statistics for continuous endpoint, without any imputation for missing data. Any exception will be clarified as a note in the related tables.

## **4.8 INTERIM ANALYSES**

One interim analysis is planned, when all enrolled patients have completed 6 months of observation, to have a preliminary evaluation of results and to assess if some parameters need to be analyzed more or less in depth.

Due to the observational nature of this study, no adjustments will be done for the derivation of the p-values of the proposed statistical tests.

This SAP could be update after the interim analysis.

**5. CHINA SUBGROUP ANALYSIS**

NA

**Research Question and Objectives****Objectives**

The primary objective for this study is to document physical activity, particularly in terms of active minutes, steps count and Metabolic Equivalent of Tasks (MET) over the 12 months period, by age categories (12-17, 18-30 and 31-50 years) in patients with haemophilia A without inhibitors receiving standard of care treatment.

The secondary objectives for this study are as follows:

- To document physical activity, particularly in terms of active minutes, by ages categories (12-17, 18-30 and 31-50 years), by type of physical activity and by intensity (as per fitness tracker default categorization);
- To describe the observed population in terms of:
  - Number of patients who are adherent to World Health Organization (WHO) Guidelines (*i.e.*, Global Recommendations on Physical Activity for Health) for the definition of physical activity;
  - Number and type of bleeds occurring during routine clinical practice and reported at any occurrence via the electronic Patient-Reported Outcome (ePRO) application;
  - Treatment regimen for haemophilia A (prophylaxis, preventative treatment before physical activity, treatment for any episode of bleeds), in terms of type of regimen (on-demand vs. prophylaxis), product used and dose;
  - Health-Related Quality of Life (HRQoL) and health status (evaluated at baseline, every three months, and at the end of the study) reported during routine clinical practice, measured using the European Quality of Life-5 Dimensions (EQ-5D-5L) score (adults/adolescents);
  - Dose and frequency of concomitant medications taken to control pain (*e.g.*, nonsteroidal anti-inflammatory drugs [NSAIDs], painkillers);

- Joint health status of enrolled patients, based on Haemophilia Joint Health Score (HJHS) questionnaire (evaluated at baseline, at six months, and at the end of the study);
- Body Mass Index (BMI) evaluated at baseline and every three months;
- Number of days away from school (patient) and/or work (patient and caregiver), and age of possible early retirement (caregiver) during the observation period, evaluated through administration of questions (evaluated at baseline, every month, and at the end of the study);
- Number of hospitalization days (patient) during the observation period evaluated through administration of questions (evaluated at baseline, every month, at the end of the study);
- Pain intensity measured using a Visual Analogue Scale (VAS) (evaluated at baseline, every month, and at the end of the study);
- To evaluate adherence to the treatment regimen:
  - Documented during planned visits according to source data (ePRO data) in electronic Case Report Forms (eCRF) by the Investigator;
- To describe the active vs. sedentary haemophiliac patients in terms of:
  - Severity of disease;
  - Annualized Bleeding Rate (ABR);
  - Pain and use of painkillers;
  - Drug regimen adopted;
  - HRQoL;
  - Hospitalization/missed days at school; - Joint Health Status.
  - To describe severe vs. moderate haemophiliac patients for the above mentioned items.

